5.2.11. Short Physical Performance Battery (SPPB)

The SPPB is an objective assessment tool developed by the National Institute on Aging for evaluating lower extremity functioning in older persons. The SPPB consists of three assessments: (1) repeated chair stands; (2) balance tests (side-by-side, semi-tandem and tandem balance tests); and (3) an eight-foot walk test. The assessments will be performed by trained study coordinators using the “SPPB Guide” administration app.

5.2.12. Pulmonary Function Test

Spirometry, lung volumes, and diffusion capacity of carbon monoxide (DLCO) will be performed in all participants. Total lung capacity will be done by body plethysmography.

5.2.13. Cardiopulmonary Exercise Test

All participants will undergo cardiopulmonary exercise testing unless they meet one of the following exclusion criteria: (1) unstable angina; (2) history of exertional syncope (unless the underlying cause has been treated); (3) history of exercise-induced sustained ventricular arrhythmia; (4) resting systolic blood pressure ≥ 200 mmHg.

We will use a semi-recumbent exercise protocol in conjunction with expired gas analysis to assess oxygen consumption uptake (VO_2) during exercise. Exercise acquisitions may be modified depending on equipment availability at each site. Participants will perform a maximal exertion-limited exercise test using a graded-exercise protocol. The protocol will consist of resting assessment of metabolic rate for 4 minutes, followed by exercise with zero (or equipment-minimal) resistance for a period of 3 minutes. Resistance will then begin at 20W for 3 minutes, increasing by 20W every 3 minutes thereafter to the endpoint of exhaustion. Breath-by-breath information will be recorded. Total work performed will be computed and exercise efficiency will be defined as total work/total oxygen consumed starting at 1-minute into the incremental ramp portion of exercise. The total length of the bicycle exercise test will depend on the participant and how long they are able to exercise. We will also continuously monitor each participant's heart rate and rhythm with electrocardiography, and blood pressure will be checked during each stage of exercise. We will also monitor the oxygen levels in their blood using a pulse oximeter. The cardiopulmonary test will be performed by trained and qualified personnel.

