3.3.3. Exclusion Criteria (HeartShare Deep Phenotyping Cohort)

The following exclusion criteria apply to both HFpEF and non-HFpEF group participants, unless otherwise indicated.

1. Life expectancy estimated to be < 1 year.
2. Primary cardiomyopathy (including amyloid, hypertrophic cardiomyopathy, cardiac sarcoidosis, hemochromatosis, or other infiltrative cardiomyopathies) or pulmonary arterial hypertension (WHO Group I, III, or IV pulmonary hypertension).
3. Any prior known left ventricular ejection fraction $< 40\%$, except if this occurred only in the setting of an acute tachycardia episode (e.g., acute atrial fibrillation).
4. Clinically significant valvular heart disease defined as:
 - a. Moderate to greater aortic stenosis, pulmonic stenosis, or tricuspid stenosis.
 - b. Any mitral stenosis.
 - c. Moderate or greater aortic regurgitation.
 - d. Greater than moderate mitral regurgitation.
5. Any planned cardiac surgery or cardiac intervention in the next 3 months.
6. Alternative primary reason for symptoms of shortness of breath and exercise intolerance in HFpEF participants in the opinion of the enrolling investigator.
7. Cardiac surgery, acute coronary syndrome, percutaneous coronary intervention, stroke, transient ischemic attack, or carotid intervention in the preceding 6 months prior to enrollment.
8. Known symptomatic epicardial coronary artery disease that is not revascularized.
9. Any non-elective hospitalization in the preceding 2 weeks.
10. Prior history of solid organ transplantation.
11. Prior history of chronic infection (HIV, hepatitis C, hepatitis B, tuberculosis) unless treated and not clinically active in the opinion of the enrolling investigator.
12. Prior history of mechanical circulatory support.
13. Prior history of non-cardiac cirrhosis.
14. Estimated GFR < 20 ml/min/1.73m² or currently on dialysis.
15. Any condition that may preclude participation or adherence to the study protocol, in the opinion of the enrolling investigator.
16. Inability to provide written consent to the study.

17. Current acute decompensated heart failure.
18. Currently pregnant.
19. Uncontrolled heart rate (>110 bpm) at the time of screening.

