5. STUDY PROCEDURES

5.1. Study Visits

Once consented, all study participants will undergo a 2-day baseline visit. Depending on the scheduling systems, physical location, and availability of the various tests required for the study, centers may split each of these visits into more than 2 days or rearrange the order of procedures, but in all cases, the duration of testing will closely approximate the details in **Table 1**. The in-person and remote data collection components of the baseline visit must occur within

a 30-day window. Thereafter, participants will receive two short surveys monthly and several longer surveys every 6 months via Eureka (see Supplementary Tables 2 and 3).. Participants will return to the Clinical Center for an in-person follow-up visit one year after the baseline visit. The one-year follow-up visit will be much shorter than the baseline visit. 2 lists the schedule of events (all components of the deep phenotyping study visits and and remote data collection instruments).

Table 1. Duration of Deep Phenotyping Study Components

Duration	Study component
Prior to baseline visit	
20 minutes	eConsent (to be done in person for participants who request it)
30 minutes	Telephone survey for medication reconciliation and medical history (in person if no prior eConsent)
Day 1 (begin fasted)	
15 minutes	Blood & urine
30 minutes	EndoPAT (peripheral arterial tonometry)
30 minutes	12 lead ECG, vitals, waist and hip circumference
30 minutes	Snack
30 minutes	Pulmonary function tests
20 minutes	Arterial tonometry (for arterial stiffness and pulsatile hemodynamics assessments)
90 minutes	Cardiopulmonary exercise testing + echo (rest + exercise)
30 minutes	Eureka questionnaires (if not done prior the study visit)
30 minutes	Education on Eureka, Kardia, and 24-hour BP devices and remote study procedures and geolocation + light lunch
Day 2	
15 minutes	6-minute walk test
60 minutes (scan time 15 minutes)	CT (chest, abdomen, thigh)
120 minutes (scan time 60 minutes)	Cardiac MRI
25 minutes	Cognitive testing
10 minutes	Short Performance Physical Battery
60 minutes	Lunch
90 minutes	Skeletal muscle biopsy (optional), adipose biopsy (optional)

Total time for Day 1: ~5 hours

Total time for Day 2: ~3 hours, 45 min (total time = ~5 hours, 15 min with optional biopsies)

Table 2. Schedule of Events

Assessment/Activity	Baseline	Monthly surveys via Eureka	6-month surveys via Eureka	12-month Follow-up visit* (In-Person)
In Person Visits				
eConsent	(X)			

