5.2.6. Laboratory Measurements

- **Blood:** All consented participants continuing to meet the screening criteria will undergo baseline blood draws after an overnight fast. Cells, serum, and plasma will be collected. Laboratory tests will include (but not limited to): complete blood count (CBC), complete chemistry panel (sodium, potassium, chloride, carbon dioxide, blood urea nitrogen, creatinine, glucose, ALT, AST, alkaline phosphatase, and total bilirubin), cystatin C, NT-proBNP (or BNP, based on local lab availability), and hemoglobin A1c. HeartShare biorepository and genetics samples will also be obtained. Whole blood samples for DNA and blood stored in RNA stabilization tubes (e.g., PaxGene) will be collected at the baseline examination and stored for future genetic analyses. Whole genome sequencing, proteomics, metabolomics, DNA methylomics, and peripheral blood mononuclear cell transcriptomics will be performed. Blood for RNA will be collected at the baseline examination and stored for future analyses in PAXgene tubes. RNA sequencing will be performed to study gene expression.
- **Urine:** We will obtain a urine sample from each participant. Urine tests will include (but not limited to): urinalysis and urine albumin to creatinine ratio. Urine will be aliquoted into 3 ml samples and frozen for future batched assays. We will check a urine pregnancy test on all pre-menopausal female participants before performing any radiographic procedures in order to exclude the possibility of radiation exposure to a fetus.

- **Stool:** Stool will be collected at home by the patient using a standardized microbiome collection kit. The sample will then be sent by the patient in a prepaid shipping container to the microbiome core laboratory.
- **Saliva:** Saliva will be collected at home by the patient using a standardized microbiome collection kit. The sample will then be sent by the patient in a prepaid shipping container to the microbiome core laboratory.

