7.3.8. Six-Minute Walk Test

Risks of this test include shortness of breath and chest tightness, and rarely, faintness or palpitations due to arrhythmias. We will guard against these by asking the participants questions before the test to determine whether it is safe for them to have this test. During the test, participants are closely monitored by study staff and the participant can stop and rest at any point during the test.

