7.3.9. Short Physical Performance Battery (SPPB)

Risks of the SPPB include shortness of breath and rarely, lightheadedness or loss of balance. We will guard against these by asking the participants questions before the test to determine whether it is safe for them to perform this test. During the test, participants are closely monitored by study staff, and the participant can stop and rest at any point during the test.

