7.3.11. Cardiopulmonary Exercise Test

During exercise test, the patient may feel muscle soreness or fatigue, shortness of breath, abnormal blood pressure, or fainting. Rarely exercise can cause irregular heart rhythms, heart attack, stroke, or sudden cardiac death. Participants may become uncomfortable during the exercise test. It is expected that they will become tired and short of breath, and that the patient's blood pressure, heart rate, and other vital signs will change as a result of exercise. The risk of an adverse event occurring is the same or lower in the exercise laboratory as it would be if they exerted themselves elsewhere. Monitoring during exercise permits supervising staff to stop tests prior to when a patient may stop, which lowers the likelihood of an adverse event compared to the participants exercising at home on their own. Participants will be closely monitored throughout the entire period by individuals who are trained to respond if the aforementioned situations that might develop.

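### When baseline testing is split or reordered, the four-item list in Protocol 5.2.13 does not withhold the maximal exercise test for a recent admission, acute decompensation or heart rate above 110 bpm

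*Protocol*

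**What the plan says.** **The rule for the exercise test.** Protocol 5.2.13: "All participants will undergo cardiopulmonary exercise testing unless they meet one of the following exclusion criteria". The four criteria are unstable angina, exertional syncope whose cause is untreated, a history of sustained ventricular arrhythmia on exercise, and resting systolic pressure of 200 mmHg or more. The test is graded and continues to exhaustion.

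**The cohort exclusions.** Section 3.3.3 excludes, among others:
- item 9: "Any non-elective hospitalization in the preceding 2 weeks"
- item 17: acute decompensated heart failure that is current
- item 19: "Uncontrolled heart rate (>110 bpm) at the time of screening"

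**The re-check.** Section 5.2.6: "All consented participants continuing to meet the screening criteria will undergo baseline blood draws after an overnight fast". This is the only place where the protocol says that eligibility is looked at again after consent.

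**The schedule.** Table 1 puts the blood draw first on Day 1 and the exercise test later the same day. Section 5.1 adds that "centers may split each of these visits into more than 2 days or rearrange the order of procedures", and requires the in-person and remote baseline components together to fall within 30 days.

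**The concern.** The exercise test is the most demanding procedure in the protocol. Section 7.3.11 names heart attack, stroke and sudden cardiac death among its rare risks. Three conditions that make someone unsuitable for the cohort on entry are missing from the list that decides who is exercised. That list is worded as complete: everyone is tested unless one of the four items applies. By contrast, the MRI section (5.2.15) leaves room for any contraindication.

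The gap does not matter while the eligibility re-check and the exercise test fall on the same morning. It matters once a center uses the freedom in 5.1. A participant who becomes unstable after the draw then meets none of the four criteria, and the written rule sends that person to the test. What is at stake is individual safety on the test day, not the validity of any analysis.

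**Working it through.** The protocol gives no figure for this point. The check compares the lists and then works through the timing.

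**1. Overlap of the two lists**

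| 3.3.3 condition | Named in 5.2.13? | Timing as worded in 3.3.3 |
|---|---|---|
| Item 9, unplanned admission | No | look-back of 2 weeks, reference date not stated |
| Item 17, acute decompensation | No | current |
| Item 19, heart rate >110 bpm | No | fixed to screening |

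The overlap is 0 of 3.

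**2. Default order (Table 1, Day 1)**

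The slots before the exercise test are blood and urine 15, EndoPAT 30, ECG and vitals 30, snack 30, pulmonary function 30 and arterial tonometry 20 minutes.

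- Start of draw to start of exercise test: 15 + 30 + 30 + 30 + 30 + 20 = 155 minutes.
- ECG and vitals end at 15 + 30 + 30 = 75 minutes, which is 155 − 75 = 80 minutes before the exercise test.

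On this schedule the 5.2.6 re-check is recent enough, and a resting heart rate has just been taken. There is no gap.

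**3. Split order**

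Let *g* be the number of days from draw to exercise test. The protocol states no value for *g*. The 30-day window is only an outer limit, and it covers remote components as well. At the draw, item 9 sees the 14 days before the draw. On the test day, the relevant period is the 14 days before the test. The share of that period which the draw-day check could not have seen is min(*g*, 14)/14:

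- *g* = 1: 1/14 = 7%
- *g* = 7: 7/14 = 50%
- *g* = 14 or more: 14/14 = 100%

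Items 17 and 19 describe a present state, so a check made on any other day says little about them.

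**4. Reordered, with the exercise test before the draw**

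The 5.2.6 re-check has not yet taken place. The last stated eligibility assessment is then the one at enrollment.

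**5. What a deferral does to the window**

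Count days from the start of the baseline window, and assume that the 2-week look-back runs from discharge. A stay that ends after day 30 − 14 = 16 cannot clear the look-back inside the window. For example, discharge on day 20 clears on day 20 + 14 = 34, which is 4 days late. A rule that only says to defer would therefore be incomplete.

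No participant count is computed, because the share of split or reordered visits is not given.

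**The case against.** The strongest reply is that the 5.2.13 list adds to the cohort exclusions and does not replace them. Items 9 and 17 are not worded as tied to screening. Section 5.2.6 shows that eligibility is meant to persist after consent. Item 15 of 3.3.3 lets the investigator exclude for any condition that may preclude participation, and 3.8 allows withdrawal for safety. Trained staff run the test under continuous ECG after a 4-minute rest phase, so a rate above 110 bpm would be seen before loading. Section 7.3.11 adds: "Monitoring during exercise permits supervising staff to stop tests prior to when a patient may stop". Sections 8.5 and 8.6 require notification and referral when serious problems emerge. Core-laboratory manuals, which are not shown, may already contain test-day checks.

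Most of this stands, and it is why the exposure is small. It does not close the gap. Withdrawal under 3.8 is discretionary and removes the person from the study; it does not postpone a test. Monitoring acts once the test is under way. None of these provisions is a written instruction to hold the exercise test for the three conditions on the day.

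A reader might go further and infer two things that the protocol does not support:

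- **That the milder tests are better protected.** For the walk test, 7.3.8 promises "asking the participants questions before the test to determine whether it is safe for them to have this test", and 7.3.9 says nearly the same for the SPPB: "asking the participants questions before the test to determine whether it is safe for them to perform this test". However, the four-item list in 5.2.13 is itself a pre-test gate, and it is more specific than those unnamed questions. Applying it already requires symptoms and blood pressure to be assessed beforehand.
- **That contrast MRI is similarly exposed to undetected pregnancy**, because the urine test in 5.2.6 is timed to radiographic procedures. Table 1 lists CT before MRI, pregnancy is a cohort exclusion (item 18), and 5.2.15 requires standard MRI safety screening. That point is largely covered.

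**Conclusion.** The point holds as a minor one. On schedules that 5.1 expressly permits, the closed list in 5.2.13 does not withhold a maximal test for a recent unplanned admission, current acute decompensation or a heart rate above 110 bpm. On the default schedule nothing is wrong.

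The conclusion rests on reading the list in 5.2.13 as complete, as its wording suggests, and on the re-check in 5.2.6 belonging to the draw alone. If a core-laboratory manual already requires a test-day check of these conditions, the change only brings the protocol into line with practice.

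The number of participants affected cannot be derived and is probably very small. The sample size and power tables in 6.2 do not change. It would be wrong to infer a major safety defect, or that the protocol intends to exercise people who are acutely unwell. The existing safeguards make that outcome remote.

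**What to change.** In 5.2.13, add 3.3.3 items 9, 17 and 19 to the list, assessed on the day of the exercise test, and state that the test is deferred if any is present. Add one sentence for deferrals that would run past the 30-day baseline window: either allow an out-of-window test, flagged as such, or record the test as not done for medical reasons.

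The cost is a short wording change. Heart rate is already available from the rest phase, and the other two items need a brief question or chart check. The downside is that a few tests will be deferred or missed. Recording the reason lets the analysis distinguish these from other missing exercise data.

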5.2.14. Cognitive Test

Cognitive testing will be performed using the Montreal Cognitive Assessment (MoCA). The MoCA test is a highly sensitive tool for early detection of mild cognitive impairment. It quickly and accurately assesses short term memory, visuospatial abilities, executive functions, attention, concentration, and working memory, language, and orientation to time and place. The MoCA test takes about 15 minutes to administer.

5.2.15. Cardiac Magnetic Resonance Imaging

Cardiac and limited liver MRI with gadolinium contrast will be performed on all participants unless contraindicated for assessment of cardiac structure and function, focal and diffuse myocardial fibrosis, aorta and pulmonary artery measurements, and liver fat. Non-contrast MRI will be performed in participants with $eGFR < 45$ ml/min/1.73 m², and those with gadolinium allergy (or any other contraindication to gadolinium). Participants with pacemakers or defibrillators will be eligible for MRI if allowed by each site's institutional protocols for MRIs with such devices.

All scanning will be carried out on a 1.5T MRI scanner. Upon arrival, participants will undergo standard MRI safety screening. An intravenous catheter will be placed in the arm and a small amount of blood (approximately 5 mL) will be collected to test renal function (creatinine; for calculation of $eGFR$) and hematocrit if no recent value is available, or as indicated at each Clinical Center's cardiac MRI protocol. Participants will then be placed on the MRI scanner, ECG electrodes will be placed on the chest to allow cardiac gating, ear plugs will be inserted into or headphones will be placed over the participants' ears to protect the participants' hearing and allow communication between the patient and MRI technologist, and the participant will be provided a squeeze ball that alerts the technologist if the participant wishes to discontinue the test at any time. The participant will be advanced, head-first, into the bore of the scanner. Localizers/scouts will be performed, and the table will be withdrawn from the scanner bore

temporarily. The participant will be advanced back into the scanner bore and IV administration of a gadolinium-based contrast agent will occur: Gadobutrol (Gadavist) at 0.10 mmol/kg total dose. This is the approved dose by the FDA. There are risks associated with use of the contrast agent, which are detailed in the consent form for the participant, and in the participant risk section below. The participant will be advanced back into the scanner bore and images will be acquired. Once imaging has been completed, the IV catheter will be removed, and a temporary bandage will be placed at the site of venipuncture.

5.2.16. Resting and Exercise Echocardiography

All study participants will undergo comprehensive 2-dimensional (2D) echocardiography with Doppler and tissue Doppler imaging (TDI) at rest in the supine and left lateral decubitus positions. A cardiac ultrasound system with harmonic imaging will be used for all echocardiographic examinations. A limited vascular (carotid and femoral) 2D and Doppler interrogation may be performed at sites that have the ability and equipment (i.e., vascular linear probes). During the cardiopulmonary exercise test (see above, section 5.2.12), exercise echocardiography will be performed during semi-recumbent bicycle exercise. Images will be obtained at each stage of exercise. Cardiac structure/function will be quantified at rest and during each stage of exercise as recommended by the American Society of Echocardiography. LV and RV structure/function, LV diastolic function, atrial size/function, hemodynamics, and speckle-tracking strain parameters will be measured at rest and at each stage of exercise. Exercise acquisitions may be modified depending on equipment availability at each site. Blood pressure will be measured using a digital BP monitor. BP at rest and at each stage, and total exercise capacity, will be recorded.

5.2.17. Computed Tomography

Participants will undergo non-contrast CT scanning of the chest, abdomen, pelvis, and upper thighs. Experienced and trained technologists will perform CT scans in each consenting participant in order to obtain an accurate and reproducible assessment of body composition (visceral fat, subcutaneous fat, and lean body mass), aortic and coronary calcium, aortic geometry, and parenchymal lung disease.

5.2.18. Tissue Biopsies (optional)

Patients who take blood thinners (for example, warfarin or novel oral anticoagulants) may be asked to stop or reduce these medications during the week leading up to a tissue biopsy procedure. For both muscle and adipose tissue collection, participants will be given printed instructions on how to prepare for the day of the tissue collection and how to care for the collection sites after the procedure. Follow-up phone calls will be made approximately a week after the procedures to assess healing of the collection sites.

